[figure not shown]

[figure not shown]

## **2. LIST OF ABBREVIATIONS**

Include a list of all abbreviations used in the TSAP

Term	Definition / description
AE	Adverse event
ALT	Alanine Aminotransferase
AST	Aspartate Aminotransferase
BI	Boehringer-Ingelheim
BMI	Body Mass index
BRPM	Blinded report planning meeting
BSA	Body Surface Area
CRF	Case Report Form
CI	Confidence Interval
CT	Concomitant Treatments
CTP	Clinical Trial Protocol
CTR	Clinical Trial Report
DM&SM	Boehringer Ingelheim Data Management and Statistics Manual
E	Efficacy
ECG	Electrocardiogram
EMA	European Medicines Agency
EOT	End of treatment visit
ERS	European Respiratory Society
FVC	Forced Vital Capacity
HR	Heart rate
HRCT	High Resolution Computerized Tomography
ICH	International Conference on Harmonisation
IPF	Idiopathic Pulmonary Fibrosis
IPV	Important Protocol Violation
IXRS	Interactive phone/web Response System
MQRM	Medical Quality Review Meeting
N	Number of patients
NA	Not Applicable

---

Proprietary confidential information © 2017 Boehringer Ingelheim International GmbH or one or more of its affiliated companies

---

Term	Definition / description
OC	Observed Case
PN	Preferred Name
PT	Preferred term
PV	Protocol violation
S	Safety
SD	Standard deviation
SDG	Standardised Drug Groupings
SEM	Standard Error of the Mean
SOC	System Organ Class
SSC	Special Search Category
TS	Treated Set
TSAP	Trial statistical analysis plan
ULN	Upper Limit of Normal

### **3. INTRODUCTION**

As per ICH E9 (5), the purpose of this document is to provide a more technical and detailed elaboration of the principal features of the analysis described in the protocol, and to include detailed procedures for executing the statistical analysis of the primary and secondary variables and other data.

This TSAP assumes familiarity with the Clinical Trial Protocol (CTP), including Protocol Amendments. In particular, the Trial Statistical Analysis Plan (TSAP) is based on the planned analysis specification as written in CTP Section 7 “Statistical Methods and Determination of Sample Size”. Therefore, TSAP readers may consult the CTP for more background information on the study, e.g., on study objectives, study design and population, treatments, definition of measurements and variables, planning of sample size, randomization.

In the following, the term ‘parent trial’ refers to 1199.32 or 1199.34 trial. All the following analyses mentioned in this TSAP concern 1199.33 data.

Interim outputs will be produced in the scope of the submission of Nintedanib in IPF. These are detailed in [Section 9.2](#).

SAS® Version 9.2 (or later) will be used for all analyses.

#### **4. CHANGES IN THE PLANNED ANALYSIS OF THE STUDY**

Although not planned in the CTP, the time to liver enzyme elevation will be analysed in this study.

As per CTP amendment 2, regular interim analyses every 48 weeks have been cancelled, but some interim analyses may be done upon request from Health Authorities or for publication purposes.

## **5. ENDPOINTS**

### **5.1 PRIMARY ENDPOINTS**

The primary focus is on safety endpoints. Please refer to CTP Section 5.1.1.

[figure not shown]
[figure not shown]
### **5.2 SECONDARY ENDPOINTS**

[figure not shown]
[figure not shown]
#### **5.2.1 Key secondary endpoints**

[figure not shown]
[figure not shown]
Not applicable.

[figure not shown]
#### **5.2.2 Other Secondary endpoints**

Not applicable.

## **6. GENERAL ANALYSIS DEFINITIONS**

### **6.1 TREATMENT(S)**

For treatment specifications, see Section 4 of CTP.

The following periods of interest will be defined: previous trial, between trials, screening, off-treatment, treatment period, post-treatment, follow-up and post-study as follows:

Note: the last day of each of the following periods is excluded.

- Previous trial: from screening in parent trial to the last trial drug intake in parent trial plus 28 days plus one day / or to the date of trial completion in parent trial plus one day / or to date of informed consent in 1199.33, whichever occurs later
- Between-trials: from end of previous trial period (see above) to date of informed consent in 1199.33
- Screening: from date of informed consent in 1199.33 to first trial drug intake in 1199.33
- Treatment period: from first trial drug intake in 1199.33 (or re-start of treatment if interruption) to last trial drug intake (or date of interruption if interruption) plus one day
- Off-treatment: from date of start of interruption to re-start of treatment
- Post-treatment: from the last trial drug intake plus one day to last trial drug intake plus 28 days plus one day
- Follow-up: from last trial drug intake plus 28 days + one day (after post-treatment period) to date of trial completion plus one day. This period is only created if last trial drug intake took place more than 28 days before trial completion.
- Post-study: from the last trial drug intake plus 28 days plus one day to database lock or from the date of trial completion (after follow-up period) plus one day to database lock, whichever occurs later

Most treatment periods are optional (e.g. “Between-trials”, “Screening” and “Follow-up” will not concern all the patients).

For safety analyses ([Section 7.8](#)), data from first trial drug intake in 1199.33 up to 28 days after last trial drug intake (included) will be considered as on-treatment period.

## 6.2 IMPORTANT PROTOCOL VIOLATIONS

The following table defines the different categories of important protocol violations (IPV) to be considered. Important efficacy IPVs are those that can potentially influence outcome measures. Important safety IPVs are those that potentially affect the rights or safety of study subjects. All these important protocol violations are listed with appropriate flags indicating their potential impact on the analyses. No patients will be excluded from the analyses based on those IPVs as no per protocol analysis is planned. Important protocol violations will be described only.

Table 6.2: 1 Important protocol violations

Category/ Code	Description	Requirements	Efficacy( E) or Safety (S)
A	Entrance criteria not met		
A1	Inclusion criteria not met		
A1.7	Parent study not completed	Inclusion criteria 2 not met (or parent trial not completed or follow-up visit in parent trial not performed, as per definition of inclusion criteria 2, but according to other CRFs information)  Automatic IPV	E
A2	Exclusion criteria not met		
A2.1	Laboratory values indicate additional risk: > 3 X ULN for AST, ALT and >2xULN for Bilirubin	Laboratory values for AST, ALT or Bilirubin out of protocol defined ranges with no elevation recorded at end of parent trial, or exclusion criteria 1 or 2 not met  Manual IPV	S
A2.3	Patient with other disease(s) which are excluded as per exclusion criteria	Exclusion criteria 3-4-5-8 not met  Automatic IPV	S
A2.4	Forbidden previous therapy	Exclusion criteria 7 not met  Manual IPV	E
A2.5	Time period between parent trial and Visit 2 not observed	Exclusion criteria 6 not met / Time period > 12 weeks between last trial drug intake of the parent trial and Visit 2 of this study  or  Visit 1 did not occur at least one day after the Follow-up Visit of the parent trial  Automatic IPV	S

Table 6.2: 1 Important protocol violations (cont'd)

B		Informed consent		
	B1	Informed consent not given or given too late	Inclusion criteria 1 not met and / or informed consent date missing  OR  Informed consent date was after Visit 1 date  Manual review of MQRMs listings	S
C		Trial medication and randomisation		
	C1	Incorrect trial medication taken	Medication kit assigned at visit 2 not matching treatment dose actually received by patient  or  Medication kit received at visit 2 does not correspond to the dose to be received according to CTP (150mg bid for patients on 150 bid in parent trial)  Automatic IPV	E
	C3	Overall Compliance not between 80% and 120% inclusive	Compliance <80% or >120%  Automatic IPV	E
	C4	Drug interruption longer than 46 days ; or 93 days in the case of acute exacerbations or unrelated AEs	Automatic IPV (reviewed in MQRM listings)	E
	C6	Dose Change not in agreement with the protocol procedures (see Section 4.2.1 of CTP)	Manual review of MQRMs listings	S
	C7	Drug not permanently discontinued despite criteria of Section 3.3.4.1 of CTP met	Manual review of MQRMs listings	S
D		Concomitant medication		
	D1	Prohibited medication use during the treatment period	
 
• Investigational therapy
 
• Full dose concomitant anticoagulation
 
• Fibrinolysis
 
• Antiplatelet therapy
 
 Manual review of MQRMs listings	S

Table 6.2: 1 Important protocol violations (cont'd)

E		Missing data		
	E4	Flow chart not observed for the planning of visit 1 and 2	Visit 1 and Visit 2 occurred on the same date whereas the period between Visit 9 of the parent trial and visit 1 is > 6 weeks.  Automatic IPV	S
F		Incorrect timing		
	F1	No adequate follow-up after liver enzyme elevation (see Table 10.1.1 of CTP)	Manual review of MQRMs listings	S

Automatic PVs are those detected via an automated programming process using SAS. Manual PVs are those identified during the MQRM meeting through patient listings and/or Manuel PV log.

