4.2.1.4 Management of other adverse events

Patients who develop an uncontrolled hypertension despite appropriate antihypertensive therapy should permanently discontinue study medication.

For AEs that are assessed drug related, a dose reduction or an interruption (of maximum 4 weeks) can be considered. Re-escalation is allowed at any time after start of dose reduction if medically justified.

Proprietary confidential information.

© 2017 Boehringer Ingelheim International GmbH or one or more of its affiliated companies. All rights reserved.

This document may not - in full or in part - be passed on, reproduced, published or otherwise used without prior written permission.

For non related AEs, drug interruption may occur for no longer than 12 weeks. Nintedanib should be re-started at the same dose as it was being taken before interruption.

Summary of allowed interruption periods:

- Acute IPF exacerbations: 8 weeks maximum interruption;
- Related AEs: 4 weeks maximum interruption, then dose reduction is recommended, then re-escalation to full dose (150 mg bid) is allowed at any time;
- Unrelated AEs: 12 weeks maximum interruption.

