7.3 PLANNED ANALYSES

The treated set (TS) will consist of all patients who received at least one dose of open-label study medication.

The definition of important protocol violations (IPV) will be specified in the trial statistical analysis plan (TSAP). These IPV definitions will include consideration of important violations of entry criteria, treatment non-compliance, prohibited medications and inadequate follow-up of hepatic events.

Patients will be analysed according to their randomized treatment group in previous studies 1199.32/34, and overall.

The last available value between visit 1 and visit 2 (before first trial drug intake) will be considered as the baseline, for this extension trial.

The main statistical analyses as described below will be performed based on all data collected up to the third interim database lock date ([see section 7.4](#)). Afterwards, only adverse events and concomitant treatments listings will be provided.

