## **7.7 EXTENT OF EXPOSURE**

The data will be analysed on the Treated Set.

A summary table showing the duration on treatment (both mean and frequency in classes, see [Section 5.4.3](#)) will be performed.

A table displaying the disposition of patients and the conclusion of patients' participation, and a table displaying the primary reason for non-inclusion will be provided.

The proportion of patients on each dose actually taken at visit 2 will be displayed according to:

- randomized treatment group in parent trial (by parent trial and both combined)
- the dose actually taken at the end of parent trial (by parent trial and both combined)
- the dose actually taken at the end of 1199.33 extension trial

A summary of treatment interruption will be performed including number of patients with at least one interruption, number and reason of interruptions, as well as time to first treatment interruption in 1199.33. A similar summary will be performed for dose change.

Besides, a summary table showing the duration on actual treatment dose (both mean and frequency in classes, see [Section 5.4.3](#)) and off-treatment duration will be performed by randomized group of the parent trial. This will take into account the actual dose following dose reductions or increases.

Kaplan-Meier plots of time to permanent treatment discontinuation will be drawn by randomised treatment in parent trial and overall. Similarly, Kaplan-Meier plots will be performed for time to first dose reduction and for time to first treatment interruption by randomised treatment in parent trial and overall. No statistical tests will be performed.

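### Protocol 3.3.4.1 and 4.2.2.1 give rules of different force on withdrawal for full-dose anticoagulation or high-dose antiplatelet therapy; as a minor second point, SAP check C4 has two cut-offs for three interruption limits

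*SAP*

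**What the plan says.** **Bleeding-risk therapies**

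- Protocol 3.3.4.1 has two lists. The first gives circumstances in which study drug must be stopped for good. The second gives circumstances in which withdrawal is strongly advised; there the investigator may keep the patient on drug in special circumstances, after discussion with the patient and with the decision documented. Full-dose anticoagulation and high-dose antiplatelet therapy are in the second list. Fibrinolysis is in neither.
- Protocol 4.2.2.1 names fibrinolysis, full-dose anticoagulation and high-dose antiplatelet therapy together, and states withdrawal with no discretion.
- Protocol 4.2.1.3 lets a patient with an acute exacerbation interrupt drug for up to 8 weeks, with short-term full anticoagulation as the example.
- SAP Table 6.2:1 has two relevant safety checks. C7 is "Drug not permanently discontinued despite criteria of Section 3.3.4.1 of CTP met". D1 is "Prohibited medication use during the treatment period", and it lists full-dose anticoagulation, fibrinolysis and antiplatelet therapy.

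**Interruption length**

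- Protocol 4.2.1.4 sets three maxima: 8 weeks for acute exacerbations, 12 weeks for unrelated events, and for related events "Related AEs: 4 weeks maximum interruption, then dose reduction is recommended".
- The first list in 3.3.4.1 includes treatment interruption and refers to 4.2.1 for the cases and periods that are acceptable.
- SAP check C4, automatic and flagged as an efficacy violation, is "Drug interruption longer than 46 days ; or 93 days in the case of acute exacerbations or unrelated AEs".

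**Use of the violations**

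SAP 6.2 excludes no patient on these grounds: "Important protocol violations will be described only".

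**The concern.** The first matter is conduct. Two protocol sections govern the same patients with different force, and a third describes a situation in which full anticoagulation leads to interruption. Two sites could treat the same patient differently and each cite the protocol. The issue does not end with the main analysis: under Protocol 6.2.5, patients who continue after the final-analysis lock are treated until they meet a reason in 3.3.4 or obtain the drug elsewhere.

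The second matter is reporting. C4 is the only check in the table that puts a number of days on an interruption. Its two numbers are not the protocol's three, no tolerance is stated, and the 8-week limit has no cut-off of its own. The automatic count of over-long interruptions will therefore differ from a count made against Protocol 4.2.1.4.

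**Working it through.** **1. One patient, two sections.** Take a patient who comes to need full-dose anticoagulation, and whose investigator continues study drug and documents why.

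| Text | Status of this patient |
|---|---|
| Protocol 3.3.4.1, second list | Compliant, if the circumstances are special and the decision is documented |
| Protocol 4.2.2.1 | Not compliant: withdrawal is stated without exception |
| SAP D1 | Listed as a safety violation |
| SAP C7, if it means the first list only | Not listed |
| SAP C7, if it means both lists | Listed as a safety violation |

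The patient is captured in every case. What varies is whether the code is D1 alone or D1 with C7. Fibrinolysis behaves similarly: it is absent from 3.3.4.1 but present in 4.2.2.1 and in D1.

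**2. C4 against Protocol 4.2.1.4.** Limit in days = weeks × 7. The margin is the C4 cut-off minus the limit. The unflagged range runs from the limit plus 1 day to the cut-off, because C4 flags only durations longer than the cut-off.

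| Reason | Protocol limit | C4 cut-off | Margin | Over limit, not flagged by C4 |
|---|---|---|---|---|
| Related event | 4 × 7 = 28 | 46 | 46 − 28 = 18 (18/28 = 64%) | 29 to 46 days |
| Acute exacerbation | 8 × 7 = 56 | 93 | 93 − 56 = 37 (37/56 = 66%) | 57 to 93 days |
| Unrelated event | 12 × 7 = 84 | 93 | 93 − 84 = 9 (9/84 = 11%) | 85 to 93 days |

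The percentages are the largest possible gaps, not frequencies.

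**3. Can 46 and 93 be reproduced by one rule?** Adding a fixed grace period to 28, 56 and 84 gives:

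- +9 days: 37, 65, 93
- +18 days: 46, 74, 102
- +37 days: 65, 93, 121

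None gives 46, 93 and 93. A fixed multiplier fails too, since the ratios are 46/28 = 1.64, 93/56 = 1.66 and 93/84 = 1.11. The cut-offs do not follow from the protocol limits by one stated or obvious tolerance.

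**4. C4 and C7 on the same interruption.** Take a 60-day interruption for an exacerbation, after which drug is restarted. It is 60 − 56 = 4 days over the protocol limit and 93 − 60 = 33 days inside C4, so C4 does not flag it. By its text C7 does, because interruption beyond the permitted period belongs to the first list of 3.3.4.1. One check passes the case and the other counts it.

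This comparison uses the 4.2.1.4 limits only. Diarrhoea and liver enzyme interruptions have their own rules in 4.2.1.1 and 4.2.1.2.

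**The case against.** The strongest reply concerns the SAP. Protocol 7.3 leaves the definition of important violations to the SAP, so a cut-off wider than the conduct limit is permitted. C4 carries the efficacy flag and may be meant to find interruptions long enough to influence outcomes. Breach of the permitted period belongs to C7, which carries the safety flag. SAP 7.7 adds another view: "A summary of treatment interruption will be performed including number of patients with at least one interruption, number and reason of interruptions". All of this stands, and it makes the C4 point minor. What remains is that no tolerance is stated, the margins are uneven (18, 37 and 9 days), two different limits share one cut-off, and the relation of C4 to C7 is not described.

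On C7, its wording about permanent discontinuation echoes the first list of 3.3.4.1, so the natural reading is that list alone. That is fair, but the second list also speaks of criteria being fulfilled, and one added phrase would settle it. D1 gives no dose for antiplatelet therapy, but its title restricts it to prohibited use and 4.2.2.1 expressly allows prophylactic use, so this is a matter of wording.

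On the protocol, one could read 3.3.4.1 as the governing rule and 4.2.2.1 as a short restatement, or 4.2.1.3 as a specific exception. The protocol states no such order of precedence, so the conflict stands.

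A reader might infer that over-limit interruptions escape the violation listings, or that patients kept on anticoagulants go uncounted. The documents do not support either: C7 covers the former by its text, although by manual review, and D1 lists the latter.

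**Conclusion.** The conflict between Protocol 3.3.4.1 and 4.2.2.1 is real and should be corrected. It is confined to full-dose anticoagulation and high-dose antiplatelet therapy, with fibrinolysis named in one section only and 4.2.1.3 adding interruption as a further course. Its effect is on what sites do and on whether C7 is assigned as well as D1. No view is taken here on which clinical rule is right.

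The C4 mismatch is real but minor. The automatic check misses interruptions up to 18, 37 and 9 days beyond the limits for related events, exacerbations and unrelated events, and it can disagree with C7 on the same case. This rests on the 4.2.1.4 limits and on the SAP text available, which gives no derivation of 46 or 93.

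A reader might also infer that the safety results are biased. They are not affected by these checks: the violations exclude no one, so no effect on the primary endpoint, adverse event incidence, is claimed. How many patients fall in the unflagged ranges, or were continued under the discretion in 3.3.4.1, cannot be sized from the documents.

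**What to change.** **Protocol.** The clinical team should reconcile 3.3.4.1, 4.2.2.1 and 4.2.1.3 for anticoagulation, antiplatelet therapy and fibrinolysis, so that one rule applies or the order of precedence is stated. This needs a protocol amendment. Protocol 8.1 requires ethics and authority approval before such changes are implemented, and all three earlier global amendments were marked that way.

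**SAP, following the reconciled text.** State in C7 which list of 3.3.4.1 it applies to, and align the therapies and dose wording in D1.

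**SAP, C4 (minor).** Key the check to the three reason-specific limits of Protocol 4.2.1.4, state any tolerance for each, and say how C4 relates to C7 when both could apply to one interruption.

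The SAP cost is edits to three table rows and reprogramming of one automatic check. No new patients, visits or data are needed.

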### 6.3 PATIENT SETS ANALYSED

- Treated Set (TS):  
This patient set includes all patients coming from 1199.32/34 who were dispensed study medication and were documented to have taken at least one dose of investigational treatment.

All analyses will be performed on the Treated Set. Patients will be analysed according to their randomized treatment group in parent studies 1199.32/34 (e.g. Nintedanib 150mg or placebo), and overall (total column). The column of main interest in the tables will be the total column (overall both treatment group in parent studies 1199.32/34) as all patients are treated on Nintedanib during the extension study.

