3. DESCRIPTION OF DESIGN AND TRIAL POPULATION

3.1 OVERALL TRIAL DESIGN AND PLAN

This is a multi-centre, multi-national, prospective, open label extension clinical trial. It is planned to include approximately 750 patients with IPF who have completed 52 weeks of treatment and the follow up period of the phase III parent trials. Only patients enrolled in the parent trials (1199.32 and 1199.34) will be eligible.

After signing Informed Consent and if all eligibility criteria are met, patients will initiate treatment with nintedanib (Visit 2). Please refer to [Section 4.1.2](#) for the method of assigning patients to treatment groups.

Overall, the trial is estimated to last a total of approximately 6 ½ years. Treatment will be stopped if a reason for withdrawal is met (refer to [Section 3.3.4](#)).

Patients' participation starts once they have signed the Informed Consent form and it is concluded when they have undergone the Follow-up Visit (unless the patient is lost to follow up or informed consent is withdrawn). Adverse events are collected during all the trial period and are considered under treatment until 28 days after drug discontinuation.

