7.3.4 Safety analyses

The planned analysis is described in [section 7.3.1](#) and [7.3.3](#).

Proprietary confidential information.

© 2017 Boehringer Ingelheim International GmbH or one or more of its affiliated companies. All rights reserved.

This document may not - in full or in part - be passed on, reproduced, published or otherwise used without prior written permission.

All patients in the treated set will be included in the safety analysis. The analyses of adverse events will be descriptive in nature and will be based on BI standards. No hypothesis testing is planned.

Statistical analysis and reporting of adverse events will concentrate on treatment-emergent adverse events (in extension study), based on BI Guideline “Handling of Extension Trials”. To this end, all adverse events will be classified according to the following trial periods: previous trial, between-trials (from follow-up visit in previous trial up to date of informed consent in extension study), screening, on-treatment, post-treatment and post-study.

All adverse events with an onset date from the date of the first dose in the extension trial up to 28 days after the end of trial treatment will be assigned to the on-treatment period. Other adverse events will be assigned to the previous trial, between-trials, screening, post-treatment, or post-study period, as appropriate.

Frequency, severity, and causal relationship of adverse events will be tabulated by system organ class and preferred term after coding according to the current version of the Medical Dictionary for Drug Regulatory Activities (MedDRA).

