## **7.8 SAFETY ANALYSIS**

All safety analyses will be performed on the Treated Set.

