## 10. HISTORY TABLE

This is a revised TSAP including the following modifications to the final TSAP

Table 10: 1 History table

Version	Date (DD-MMM-YY)	Author	Sections changed	Brief description of change
Final	14-June-13	[REDACTED]	None	This is the final TSAP without any modification
Revised	29-September-15	[REDACTED]	4	As the protocol has been revised, the term "On trial survival" has already been changed into "Time to death"
			5.2.2	In accordance with new SOP, endpoints are now classified as further endpoints and not as secondary endpoints anymore.
			[REDACTED]	[REDACTED]
			[REDACTED]	[REDACTED]
			[REDACTED]	[REDACTED]
			[REDACTED]	[REDACTED]
			6.2	Precision added for IPV A2.1
			6.6	A reference to the CTP has been added for the handling of missing data.
			7.5.2	In accordance with new SOP, endpoints are now classified as further endpoints and not as secondary endpoints anymore.
			[REDACTED]	[REDACTED]
			7.7, 7.8.1	Precision that KM plots will also be performed overall groups and with 70% cut-off for y-axis for AEs of particular note
			[REDACTED]	[REDACTED]
			General	Reference section numbers have been updated or removed due to new classification of endpoints and for consistency purposes with revised CTP based on Global amendment 2.

Table 10: 1 History table (cont'd)

Revised	19-September-16	[REDACTED]	6.3	The definition of the Treated Set has been updated in order to specify that the Treated Set only includes patients from parent trials 1199.32/34 (and not transitioned patients from study 1199.35).
				[REDACTED]
Revised	25-Jul-17	[REDACTED]	7.2	The definition of baseline therapies was clarified. A summary of post-study drug discontinuation therapies has been added in order to display the proportion of patients having taken commercial nintedanib after trial drug discontinuation.
			7.8	Some specific AE tables by Topic or syndrome were added, as judged medically relevant for the project.
				[REDACTED]
				[REDACTED]

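### The SAP narrows the protocol's Treated Set to patients from 1199.32/34, so the readable plan has no safety summary for any patient transitioned from 1199.35 and dosed in this trial

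*SAP*

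**What the plan says.** **Protocol.** Section 7.3 gives a definition with no limit by originating trial: "The treated set (TS) will consist of all patients who received at least one dose of open-label study medication". Section 7.3.4 adds: "All patients in the treated set will be included in the safety analysis". On entry, Section 3.1 states: "Only patients enrolled in the parent trials (1199.32 and 1199.34) will be eligible". Inclusion criterion 2 (Section 3.3.2) agrees, as it requires completion of 1199.32 or 1199.34. Section 1.2 describes 1199.35 only as an open-label rollover trial offered to phase II patients, and says that it is ongoing.

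**SAP.** Section 6.3 defines the set this way: "This patient set includes all patients coming from 1199.32/34 who were dispensed study medication", with the further condition of at least one documented dose. The same section says "All analyses will be performed on the Treated Set", and Section 7.8 repeats it for safety: "All safety analyses will be performed on the Treated Set". The history table entry of 19 September 2016 explains the wording: "the Treated Set only includes patients from parent trials 1199.32/34 (and not transitioned patients from study 1199.35"). SAP Section 4, which is where changes to the planned analysis are recorded, mentions time to liver enzyme elevation and the cancelled regular interim analyses. It does not mention the Treated Set.

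**The concern.** The two documents give the same name to two different sets, and that set carries the primary endpoint: the number and percentage of patients with any adverse event, serious events, events leading to discontinuation, and fatal events (Protocol Section 5.1.1). The SAP definition is narrower by design. Naming transitioned 1199.35 patients as left out of the 1199.33 set makes most sense if some were dosed in 1199.33, or were expected to be.

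At stake is completeness. The trial's one stated objective is long-term safety. A serious or fatal event in a treated 1199.35 patient would appear in no summary that the readable SAP describes, and a reader who relied on the protocol's definition would not know that anyone had been left out.

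**Working it through.** The documents give no figure for this point, so the main check is a comparison of text, followed by a range under stated assumptions.

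**1. Do the definitions differ?** Yes. Protocol 7.3 has one condition, an open-label dose. SAP 6.3 adds a second, that the patient came from 1199.32/34. They select the same patients only if nobody from elsewhere was dosed.

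**2. Is the difference current?** Yes. The history entry agrees with the present SAP 6.3 and explains it. Protocol version 4.0 (28 March 2017) came after the SAP change and added text to Section 7.3, but kept the unrestricted definition. The SAP was revised again on 25 July 2017 without recording the restriction in Section 4.

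**3. Does the readable SAP cover these patients elsewhere?** No other patient set, column or listing for them is visible. SAP Section 3 limits the term parent trial to 1199.32 or 1199.34. The total column in Section 6.3 is the two parent-trial arms combined.

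**4. How large could the omission be?** Inputs: about 750 planned patients, all from the parent trials (Protocol 3.1; the synopsis split of 600 + 150 = 750 agrees), and k patients from 1199.35 dosed in 1199.33. The value of k is assumed. An extreme ceiling is k = 432, the number randomised in phase II trial 1199.30 (Protocol 1.2), if 1199.35 drew only on that trial.

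- Share of all treated patients left out = k/(750 + k).
- If their incidence of an event differs by 10 percentage points (an assumption), the all-treated incidence moves by 10 × k/(750 + k) points.

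| k (assumed) | Share left out | Shift for a 10-point difference |
|---|---|---|
| 5 | 5/755 = 0.7% | 0.07 points |
| 10 | 10/760 = 1.3% | 0.13 points |
| 50 | 50/800 = 6.3% | 0.63 points |
| 100 | 100/850 = 11.8% | 1.18 points |
| 432 (ceiling) | 432/1182 = 36.5% | 3.65 points |

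**5. Precision for rare events.** The 95% upper limit when no event is seen is 1 − 0.05^(1/n). It is 0.399% at n = 750, 0.374% at n = 800 and 0.352% at n = 850. Adding 50 or 100 patients hardly changes it.

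**The case against.** The strongest reply is that the protocol's own population is 1199.32/34 patients throughout: the synopsis objective, Section 3.1, inclusion criterion 2, Section 7.1 and Section 7.7. For that population the two definitions select essentially the same people, and the SAP only makes the limit explicit. There is also a practical reason for it. Results are shown by randomised arm in the parent trial, and trial periods and several protocol-violation rules are tied to that trial. A 1199.35 patient has no such arm.

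This justifies keeping these patients out of the parent-arm columns. It does not justify leaving them out of every summary. SAP 6.3 makes the total column the main one because everyone receives nintedanib, and that reason applies equally to them. If they are instead seen as not meeting the entry criteria, SAP Section 6.2 says that nobody is excluded from the analyses for an important protocol violation.

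Three further limits stand. First, a reader might infer that 1199.35 patients were certainly treated in 1199.33 and dropped from every safety analysis. The documents do not support that. Dosing is implied by one history entry. The history row after it is redacted, the contents list has a blanked entry between SAP 6.3 and 6.5, and some cited SAP sections are not visible, so separate handling may exist. Second, a reader might infer that these patients have the longest prior exposure. This is not shown: 1199.30 included placebo and lower-dose arms, and no exposure time in 1199.35 is given. Third, collection and expedited reporting of adverse events under Protocol Section 5.3.7 does not depend on the Treated Set. Only their place in the trial's summaries is in question.

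**Conclusion.** The point holds as a mismatch between protocol and SAP, with a conditional gap in reporting. The Treated Set is defined in two ways in current text, the narrower version is deliberate, SAP Section 4 does not record it, and the protocol has no entry route for the patients whom the SAP sets aside. If any of them were dosed in 1199.33, the readable SAP summarises none of their adverse events.

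The size cannot be fixed, because their number is not stated. The effect on incidence and precision is probably small unless the number is large, and all analyses are descriptive, so no error rate is affected. What matters is that serious and fatal events are fully accounted for in a long-term safety trial. The change should be made. Confidence is medium, because the conclusion rests on an inferred transition and on a SAP that is partly redacted.

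**What to change.** 1. Keep the 1199.32/34 set for the parent-arm columns and their total.
2. Add a separate descriptive summary for patients transitioned from 1199.35, giving their number and the four primary categories (any adverse event, serious, leading to discontinuation, fatal), with an all-treated total that matches Protocol 7.3. If such a summary already exists in text that is not visible, SAP 6.3 need only point to it.
3. List the restriction and its reason in SAP Section 4.
4. Reconcile the Treated Set definition in Protocol 7.3 and the eligibility wording in Protocol 3.1 and 3.3.2 with the transition. If no 1199.35 patient was dosed in 1199.33, say so, and the added summary is not needed.

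The cost is one set flag, one extra summary and some wording changes. The drawback is a slightly more mixed all-treated column, but the unchanged 1199.32/34 total beside it lets readers see the difference.
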